#### Detection of increased depression.

A major activity of the Board will be to determine if subjects are developing depression at an unusual rate during their time in the project. Removal of subjects from the study is included in the responsibilities of the PI. Study continuation is the duty of the ISMC and rests, in part, on the collected data pertaining to incidence of new depression in this subject population.

### 7.5: Follow-up for Adverse Events

The Study Psychologist will investigate AEs related to participant mental health and make appropriate referrals for further care. The Study Psychologist will follow-up with the parent to assess follow-through within one week of the reported event. The Project Manager will investigate all other AEs and follow up with the participant until stable.

### 7.6: Safety Monitoring (See [DSMP](#))

An Independent Safety Monitoring Committee (ISMC) will be constituted with a charter describing membership, meeting frequency, review process, report generation, liaison with the PI and research team, range of recommendations and criteria for subject removal and program suspension.

ISMC membership should include: a psychologist with expertise in depression, a psychologist/psychiatrist with a research/statistical background, and an individual with expertise in mindfulness. None of these individuals will be directly associated with the study other than through the ISMC.

#### 7.6.1: Frequency of Review

The ISMC will meet prior to the first group trainings, and within one month after the first full cohort of 20 subjects (10 in each group) have completed the 8 week training period. They will meet every six months thereafter or whenever the PI requests a review outside of those times. Meetings will be facilitated by the PI and project manager by providing a private meeting location and all requested materials on the day of the review. The PI and project manager will also provide a summary of the project dating from the time of the last review. The PI and other research personnel will be available to meet with the Board as requested. The ISMC will continue to meet through data collection.

#### 7.6.2: Review Materials

The ISMC will review all available data sets, AEs, SAEs and UPs, operational manuals, focus group reports, IRB submissions and renewal documentation, IRB notifications and all other materials generated by the study.

### 7.6.3: Summary report

A member of the ISMC will be designated by consensus as chairperson and will be responsible for conducting the meetings and for preparing a report after each meeting, summarizing the review along with recommendations for changes, if any, and continuation of the project. The report will be transmitted to the PI within 2 weeks of the meeting unless there is urgency, as determined by the Board, requiring action.

## 8. INTERVENTION DISCONTINUATION

---

### 8.1: Discontinuation of Intervention for a Participant

Subject may stop their participation for any reason, e.g., the subject is non-compliant with the protocol; subject develops unacceptable side effects; or psychosocial circumstances prevent continuation.

### 8.2: Possible reasons for discontinuation of the whole study

Possible reasons for discontinuation of the whole study include the following:

- Study closure by NIH institute
- Research environment is no longer supportive
- Multiple Unexpected Problems (UP)
- Insufficient recruitment
- ISMC or Study Monitor find evidence of serious safety issues. If greater than 3 enrolled and randomized subjects develop a grade 3 or greater adverse event due to the intervention, the entire study would be stopped and the ISMC will reevaluate.

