### 7.3.2: Classification of AE Severity

Classification of AEs will be based on the Common Terminology Criteria for Adverse Events (CTCAE) Version 4, 2009. AEs will be described by symptom or condition/diagnosis, and graded for severity (mild, moderate, or severe) — depending on the intensity of the event. Two additional categories will be used based on the CTCAE system, “life threatening” and “death”.

Grade 1. Mild: asymptomatic or mild symptoms; clinical or diagnostic observations only; minimal impact on subject’s life; intervention not indicated.

Grade 2. Moderate: medical care sought; significant but limited inconvenience on Activities of Daily Living (ADL) or lifestyle; local or noninvasive intervention indicated.

Grade 3. Severe: medically significant but not immediately life-threatening; disabling; limiting self-care; substantial disruption to the subject’s well-being; hospitalization or prolongation of hospitalization indicated.

Grade 4. SAE. Life-threatening consequences; urgent medical intervention indicated.

Grade 5. SAE. Death: related to AE.

An AE that is graded as severe (Grade 3) can be distinct from an SAE (Grades 4 and 5). A subject could experience a severe AE (Grade 3) that does not meet the definition of an SAE (see above). Alternatively, a subject could experience a moderate AE (fever, mild confusion) that meets the SAE definition (example - need for antibiotics to combat a life threatening infection).

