## 9.4: Interim Analyses and Stopping Rules

### 9.4.1: Study-wide stopping rules

These include the occurrence of a serious adverse event, CTCAE Grade 3 or higher, possibly related to the study protocol, occurring in 5 or more randomized adolescents. If these conditions occur, the ISMC will review and make recommendations on the advisability of continuing the study

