### 6.3.3 Severity of Event

The following scale will be used to grade adverse events:

1. Mild: no intervention required; no impact on activities of daily living (ADL)
2. Moderate: minimal, local, or non-invasive intervention indicated; moderate impact on ADL
3. Severe: significant symptoms requiring invasive intervention; subject seeks medical attention, needs major assistance with ADL

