## 6.5 Halting Rules

Study-wide stopping rules include the occurrence of a serious adverse event, CTCAE Grade 3 or higher, possibly related to the study protocol, occurring in 5 or more randomized adolescents. If these conditions occur, the ISMC will review and make recommendations on the advisability of continuing the study.

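### The protocol and DSMP state two numeric study-wide safety rules that differ on count, event class, causality and action, and nothing says which governs

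*Combined protocol and SAP*

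**What the plan says.** Protocol 8.2, in its list of possible reasons for ending the whole study, gives a numeric trigger: "If greater than 3 enrolled and randomized subjects develop a grade 3 or greater adverse event due to the intervention". The consequence is that "the entire study would be stopped and the ISMC will reevaluate".

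Protocol 9.4.1, headed as the study-wide stopping rules, gives another: "a serious adverse event, CTCAE Grade 3 or higher, possibly related to the study protocol", in 5 or more randomized adolescents. The consequence is that the ISMC considers the matter and advises whether to go on. DSMP 6.5 repeats this rule ("the occurrence of a serious adverse event, CTCAE Grade 3 or higher, possibly related to the study protocol").

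DSMP 7.3 adds a general stop for adverse effects that cast doubt on safety, with no count, grade or relatedness threshold.

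The inputs to these rules are defined twice:

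- **Severity.** Protocol 7.3.2 uses five grades based on CTCAE version 4, and its Grade 2 begins "Moderate: medical care sought; significant but limited inconvenience on Activities of Daily Living (ADL) or lifestyle". DSMP 6.3.3 uses three levels, of which the third is "Severe: significant symptoms requiring invasive intervention; subject seeks medical attention, needs major assistance with ADL".
- **Relatedness.** Protocol 7.3.3 has four categories: definitely, probably and possibly related, and definitely unrelated. DSMP 6.3.1 pools possible, probable and definite as related.

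**The concern.** A numeric safety rule is useful only if the people applying it reach the same answer from the same events. Here two rules sit in one protocol, neither cites the other, and no order of precedence is given. Staff following 8.2 and staff following 9.4.1 could disagree on whether a threshold has been crossed. If both were crossed, they could disagree on whether the study is halted first or reviewed while it continues.

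Participants are mostly minors selected for depressive symptoms, and the DSMP names major depression and suicide as expected risks. The section of protocol 7.4 on detecting increased depression makes continuation of the study the ISMC's duty, so the ISMC needs one unambiguous instruction. No efficacy estimate or analysis depends on the point. It concerns safety governance.

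**Working it through.** The plan states no event rate, probability or operating characteristic for either rule, so there is no figure to reproduce. The check is a comparison of texts, followed by an illustration of size.

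**Step 1. The rules side by side**

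| | Protocol 8.2 | Protocol 9.4.1 and DSMP 6.5 |
|---|---|---|
| Count | more than 3, so at least 4 | at least 5 |
| Share of 80 | 4/80 = 5.0% | 5/80 = 6.25% |
| Event class | any AE of grade 3 or more | serious AE that is also CTCAE grade 3 or more |
| Causality | due to the intervention | possibly related to the study protocol |
| Action | stop, then ISMC re-evaluates | ISMC reviews and advises |

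Section 8.2 is looser on count and seriousness and stricter on causality. Neither rule is a subset of the other.

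**Step 2. Three cases**

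- (a) Four teens have non-serious grade 3 events due to the intervention. Under 8.2, 4 > 3, so it is met. Under 9.4.1, the events are not serious and 4 < 5, so it is not met.
- (b) Five teens have serious grade 3+ events judged only possibly related. 9.4.1 is met. 8.2 is not met if its causal wording means more than possible.
- (c) Five teens have serious grade 3+ events due to the intervention. Both are met, and the stated actions differ.

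Case (b) cannot be settled from the text, because neither protocol 7.3.3 nor DSMP 6.3.1 places 8.2's causal wording against its relatedness categories.

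**Step 3. Size of the count difference alone**

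Assume N = 80, independent participants, and a per-teen probability p of an event that qualifies under both rules. The values of p are assumptions. Only 8.2 fires when exactly four teens are affected:

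P(X = 4) = C(80,4) × p^4 × (1−p)^76 = P(X ≥ 4) − P(X ≥ 5)

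At p = 0.05: 1,581,580 × 0.00000625 × 0.95^76 = 0.200.

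| p | P(X ≥ 4) | P(X ≥ 5) | P(X = 4) |
|---|---|---|---|
| 1% | 0.009 | 0.001 | 0.007 |
| 2% | 0.077 | 0.022 | 0.055 |
| 3% | 0.219 | 0.093 | 0.127 |
| 5% | 0.572 | 0.371 | 0.200 |
| 7.5% | 0.859 | 0.725 | 0.134 |
| 10% | 0.965 | 0.912 | 0.053 |

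**Step 4. Adding event class and causality**

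This is a simulation of 200,000 trials at an assumed 5% rate of grade 3+ events that are at least possibly related.

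| Assumption | Both | Only 8.2 | Only 9.4.1 | Neither |
|---|---|---|---|---|
| All due to the intervention, half serious | 5.0% | 52.1% | 0% | 42.9% |
| All serious, half due to the intervention | 12.8% | 1.2% | 24.3% | 61.6% |

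Which rule fires alone depends on seriousness and attribution, the two features that the rules treat differently.

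**Step 5. The inputs**

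Seeking medical care appears under Grade 2 in protocol 7.3.2 and under level 3 in DSMP 6.3.3. The DSMP's own halting rule cites a CTCAE grade, although its scale is not CTCAE. Protocol 7.3.2 labels serious events as Grades 4 and 5 while listing hospitalization under Grade 3, and protocol 7.3.1 makes inpatient hospitalization serious.

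**The case against.** The best defence is that these are separate, non-exclusive triggers: halt when events are caused by the intervention, review when they are only possibly related. The list in 8.2 is headed as possible reasons, and 9.4.1 is worded as not exhaustive. That reading is workable, and case (b) shows the review rule having an effect of its own. But the documents never state it, they leave the causal boundary undefined, and case (c) still carries two actions.

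Four stronger readings are tempting and are not supported:

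- **That the same data both stop and do not stop the trial.** 9.4.1 never says that the trial continues below five. At four teens one rule is met and the other is silent. The direct clash is on action when both are met.
- **That 8.2 always pre-empts the review rule.** This overlooks 8.2's stricter causal wording.
- **That outside 8.2 nothing happens at four teens.** Protocol 7.4 sends related or possibly related serious events to the IRB and ISMC within 24 hours and has the ISMC review all adverse events regularly. DSMP 7.3 holds a general safety stop.
- **That about 24 incident depressions (30% × 80) could cross the grade 3 line through the scale mismatch.** The >30% figure is for untreated adolescents. With 30% in 40 controls and the plan's hazard ratio of 0.52, the total is 12 + 40 × (1 − 0.70^0.52) ≈ 12 + 7 = 19. More importantly, both rules also require attribution to the intervention or the study. 9.4.1 and DSMP 6.5 also name CTCAE and require seriousness. DSMP level 3 lists invasive intervention and major help with daily activities as well, so a referral is not clearly level 3.

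On serious events, protocol 7.3.2 also says that a moderate event can be serious. The Grades 4 and 5 label is therefore loose wording and does not exclude lower-grade serious events.

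**Conclusion.** The point stands as an internal inconsistency in the current text of a safety decision rule. There are two numeric rules in three places, differing on count, event class, causality and action, with no statement of which governs. It must be fixed, because the study's halting instruction is ambiguous as written.

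The contradiction rests on the text alone and needs no assumed rate. Its practical size does: on the count alone, exactly four affected teens has a probability of 0.7% to 20% for assumed rates of 1% to 10%. The split in step 4 rests on assumed shares of serious and attributable events. Both calculations treat participants as independent, although they are taught in groups. DSMP 1.1 reports few adverse events and no serious ones in earlier similar programs, but in a general adolescent population, so low rates are plausible and not assured.

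The severity-scale and serious-event wording mismatches are real but secondary. They bear mainly on 8.2, which names no scale, and on how DSMP-graded events map to CTCAE.

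**What to change.** Reconcile protocol 8.2 and 9.4.1 with DSMP 6.5 and 7.3 into one rule set that states the count, the event class, the causality wording and the action. If two tiers are intended, say so and define the boundary between them in terms of the relatedness categories, using the same categories in protocol 7.3.3 and DSMP 6.3.1. Use one severity scale in both documents, and align the serious-event wording in protocol 7.3.2 with 7.3.1.

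Which threshold, event class and action apply is for the sponsor and the ISMC to decide; this review proposes none. The cost is a wording amendment to the protocol and the DSMP, confirmed by the ISMC and passed through the usual funder and IRB approvals. No data collection, sample size or analysis changes.

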### 8.3: Early discontinuation

Participants will continue to be followed, with their permission, for another 6 weeks if study interventions are discontinued for reasons other than the normal end of the study. Permission will be sought for questionnaire completion at stopping.

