## 1.2: Secondary Objectives

### Specific Aim 2

To test the feasibility of an exploratory clinical trial involving a mindful self-compassion intervention, the MFY program (treatment group), and a comparison attention-control among 14-17 year old adolescents (participants may turn 18 after enrollment) with subsyndromal depression. Study results will guide the development of an adequately powered clinical trial in terms of recruitment needs and logistics, equivalence of credibility of the two programs, and participants’ willingness to complete assessment instruments, adhere to study protocols, and complete the study.

#### Purpose 2

Study results will guide the development of an adequately powered clinical trial in terms of recruitment needs and logistics; subjects’ acceptance of the treatment and control programs;

equivalence of credibility of the two programs; and subjects' willingness to complete assessment instruments, adhere to study protocols, and complete the study.

### Specific Aim 3

With feasibility being tested in Aim 2, we will explore primary and secondary outcomes and mediators in response to the MFY program in Aim 3, including time to incident depression by the time of the 36-week follow-up (i.e., MDD-major depressive disorder) (primary outcome); resilience, change in depressive symptoms (secondary outcomes); and rumination, negative cognitive style, and shame (potential mediators).

#### Purpose 3

This study intends to analyze, in an exploratory fashion, the following: incident depression (primary outcome); change in depressive symptoms and resilience (secondary outcomes); and rumination, negative cognitive style, and shame (potential mediators).

Measures are collected at baseline, halfway through the 8-week course, after completion of each 8-week program, at 22 weeks post-program, and at 36 weeks post-program. Analyses are conducted to inform the planning of an adequately powered randomized controlled trial.

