## 6. STUDY PROCEDURES

### 6.1: Schedule of Evaluations

Participants will follow the schedule in Table 3 to complete consenting and assessments:

Table 3. Schedule of Evaluations												
Assessment	Visit 1 Screen and Baseline	Before Visit 2 (online)	Visit 2 (W0)	Daily (W0-8)	Visits 3-5 (W1-3)	Visit 6 (W4)	Visits 7-9 (W5-7)	Visit 10 (W8)	Visit 11-12 (W13, 17)	Visit 13 (W22)	Visit 14-15 (W27, 32)	Visit 16 FINAL (W36)
Informed Consent	X											
Demographics	X											
Enrollment	X											
Psychological	X											
Inclusion/Exclusio	X											
Questionnaires		X				X		X		X		X
Randomization		X										
Credibility			X									
Daily practice diary				X								
Weekly practice									X	X	X	X
Weekly depression			X		X	X	X	X	X	X	X	X
Focus Group								X				X
Parent measures		X						X		X		X

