## Early Discontinuation from Study Intervention

Potential reasons for early termination include:

- 1) Subject no longer interested
- 2) Adverse events
- 3) Subject not able or willing to follow the protocol
- 4) Subject moved away from the area.

If subjects withdraw early, the PI or a designee will follow-up by telephone to inquire about health status as it relates to adverse events experienced by the subject leading to early discontinuation of participation.

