### 8.4: Normal end to the study

At the end of the 8-week intervention, subjects completing that part of the study will be followed for another 36 weeks with encouragement to maintain their assigned home practice. Questionnaires will be completed at 22 weeks post-intervention (Visit 13) and 36 weeks post intervention (Visit 16).

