## 9.3: Definition of Populations

The ITT (Intent to treat) population is any participant randomized to an intervention group, whether or not he/she participates. “Per protocol” populations (“Completers”) are participants who do not formally withdraw.

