## 9.5: Outcomes

Our primary goal is to develop a depression-prevention program based on mindfulness and self-compassion and to establish the feasibility of its implementation as compared with an active attention-control comparator. Hence, the establishment of quality assurance processes and complete data documentation assume even greater importance than data analysis. Data of multiple types from multiple sources will be captured. For questionnaire assessments, secure internet-based data collection instruments will be used, accessible by internet-capable device.

Quality assurance of these measures will include review of study instruments for range and consistency checks, and descriptive analyses to assess distributions of study variables. Quality assurance of qualitative measures include 1) maintaining a spreadsheet to log scheduled, completed, transcribed, and analyzed focus groups and interviews; 2) establishing a transcription template to ensure data is uniform in appearance; 3) arranging for secure storage of recordings and transcripts on REDCap; 4) review of consistency of styles across interviewers; and 5) review of recordings to assess accuracy of transcriptions.

All statistical analyses will utilize all adolescents who were randomized to one of the intervention arms and who attended at least one class. Individuals who were unable to attend a class are excluded. Complete case analyses are planned (without imputations).

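### Outcome follow-up stops 6 weeks after a teen's program is discontinued early, although the ITT population is everyone randomized and the main outcomes are collected online

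*Combined protocol and SAP*

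**What the plan says.** Section 8.3 (Early discontinuation) follows participants, with their permission, "for another 6 weeks if study interventions are discontinued for reasons other than the normal end of the study". It adds: "Permission will be sought for questionnaire completion at stopping". Section 8.4 (Normal end to the study) covers those who finish the 8-week course: "subjects completing that part of the study will be followed for another 36 weeks". For early withdrawers, the paragraph headed Early Discontinuation from Study Intervention, at the end of section 6, provides only that "the PI or a designee will follow-up by telephone to inquire about health status as it relates to adverse events" leading to the withdrawal.

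Section 9.3 says the ITT population "is any participant randomized to an intervention group, whether or not he/she participates". Section 9.5 restricts every analysis to randomized teens who came to at least one class, and plans complete-case analysis with no imputation.

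Aim 3 (section 1.2) sets the primary clinical outcome as "time to incident depression by the time of the 36-week follow-up". Section 9.5.1 measures it with the weekly PROMIS score and analyses it by Kaplan-Meier and Cox. For SMFQ change, sections 9.5.2 and 9.6.1 plan ANCOVA, paired t-tests and longitudinal random effects models. The weekly PROMIS is given through REDCap (section 9.4.2), and the questionnaires are completed through a REDCap link (section 10.3.3).

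**The concern.** No section keeps outcome collection going to Visit 16 for a teen who stops the program. The plan names an ITT population that does not depend on participation, but its follow-up rule does. The outcomes concerned do not require the teen to be in class, so this loss comes from the follow-up rule and could be avoided.

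The loss may also be related to the outcome. The protocol's own reasons for stopping include adverse events, psychosocial circumstances and the development of major depression (the early-discontinuation paragraph in section 6, and sections 8.1 and 9.4.3). One case shows the mechanism. Under section 9.4.2, a teen with psychologist-confirmed major depression is withdrawn. If that teen's PROMIS T-score never reached 70, the time-to-event analysis in section 9.5.1 would treat the teen as censored, not as an event. The plan has no censoring rule for discontinuers and no sensitivity analysis for informative censoring.

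At stake are the exploratory between-arm estimates of Aim 3. Aim 2 is also affected, because a pilot that stops asking cannot show whether teens who leave classes would still answer online.

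**Working it through.** **Inputs from the documents.** 80 teens, 1:1, so 40 per arm. Hazard ratio 0.52 with 80% power, and untreated incidence above 30% with no time window (section 9.2.1). SMFQ-C + SMFQ-P difference 4, SD 6, with power above 80% (section 7.2 of the Data Safety Monitoring Plan). The horizon T has two readings. The schedule in section 6.1 puts Visit 16 at week 36 counted from W0. Section 8.4 puts it 36 weeks after the course, so T = 8 + 36 = 44.

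**Assumptions.** The documents give no stopping rate. I use 20% as a central value, suggested by the 80% completion criterion in section 9.6.2, with a range of 10–30%. Stopping is equal in both arms, hazards are exponential, control risk is 30%, and tests are two-sided at 5%.

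**The plan's own figures.**
- SMFQ: power = Φ(4 / (6·√(2/40)) − 1.96) = Φ(2.981 − 1.96) = 84.6%. This agrees with the stated figure of above 80%.
- Time to event: the treated risk is 1 − 0.70^0.52 = 16.9%, so expected events = 40 × (0.300 + 0.169) = 18.8. Schoenfeld power = Φ(½·√18.8·|ln 0.52| − 1.96) = 29%. The stated 80% is not reproduced at 30% risk; it would need 74 events. That is a separate matter, and 29% is used below only as the baseline.

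**Follow-up lost by a teen who stops at week t:** max(0, T − t − 6).

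| Stop at week | Lost, T = 36 | Lost, T = 44 |
|---|---|---|
| 1 | 29 (81%) | 37 (84%) |
| 4 | 26 (72%) | 34 (77%) |
| 8 | 22 (61%) | 30 (68%) |
| 12 | 18 (50%) | 26 (59%) |
| 16 | 14 (39%) | 22 (50%) |
| 30 | 0 | 8 (18%) |
| 38 | – | 0 |

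A stop at week 8 is observed to week 14. That is before Visit 13 on either reading (week 22, or 8 + 22 = 30), so both late visits are missed.

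**Person-time lost if 20% stop at week 4:** 0.20 × 26/36 = 14.4%, or 0.20 × 34/44 = 15.5%. Up to 20% of Visit 16 scores go with it.

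**Time-to-event analysis.** With early censoring, the weeks already observed are kept. Expected events fall from 18.8 to 16.2 (T = 36) or 16.0 (T = 44), and power from 29% to 26%. Across 10–30% stopping at week 4 or 8, events are 14.6–17.7 and power is 24–28%. Excluding these teens altogether would leave 15.0 events at 20%.

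**SMFQ change at a late visit, complete case:**
- 10% missing (36 per arm): Φ(2.828 − 1.96) = 80.7%
- 20% missing (32 per arm): Φ(2.667 − 1.96) = 76.0%
- 30% missing (28 per arm): Φ(2.494 − 1.96) = 70.3%

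**The case against.** The strongest reply is that the trial is a feasibility study. Section 9.1 sets statistical hypotheses aside, section 9.6.1 does not expect adequate power, and the clinical comparisons are exploratory. That stands, and it limits the severity.

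Several stronger readings are tempting, and the documents do not support them.

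- A reader might infer that complete-case analysis removes discontinuers from the primary outcome. Kaplan-Meier and Cox would normally censor them at the last PROMIS score and keep the earlier weeks. Removal applies to the SMFQ ANCOVA and paired tests.
- A reader might infer that nothing in the plan copes with missing data. The random effects models can use partial series, section 9.6.1 examines missing-data patterns, the Program Credibility paragraph compares drop-out by arm, section 9.6.2 plans telephone interviews with non-completers, and section 8.3 seeks questionnaires at stopping.
- A reader might infer that anyone who stops loses most of the window. The table shows this only for stops during the course and early continuation.
- A reader might infer that stopping is known to be driven by mood. The listed reasons also include loss of interest and moving away. A teen who reaches T = 70 before stopping already counts as an event. Informative censoring is plausible, not shown.
- A reader might infer that every outcome is online. The credibility scale is on paper, and attendance and focus groups are not online. The statement holds for PROMIS, SMFQ and BRS.

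The scope of section 8.3 is also unclear. It sits between whole-study discontinuation (8.2) and the normal end (8.4), and could be read as study-wide. It does not clearly cover a teen who misses classes without formally withdrawing. This does not rescue the plan: on either reading, no section continues outcomes to Visit 16 for a teen who stops.

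**Conclusion.** The point holds in a limited form. The follow-up rule does not match the ITT definition, and it discards data that could be collected online. For a stop during the course the loss is 61–81% of the window (36 weeks) or 68–84% (44 weeks). It falls to half for a stop at week 12 or 16, and to zero from week 30 or 38.

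The measurable cost falls mainly on late SMFQ change: about 85% power down to 76% at 20% missing, and 81–70% across 10–30%. For time to event, the loss of power is small and the issue is possible informative censoring. These figures rest on assumed stopping rates and times, equal stopping in the arms, and the premise that discontinuers would otherwise have answered; some who lost interest would not. The primary objective, feasibility, is not threatened.

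**What to change.** In section 8.3, state that the rule applies to individual participants, and separate stopping the program from stopping data collection. Continue the weekly PROMIS link and the Visit 13 and Visit 16 adolescent and parent questionnaires through Visit 16 for every randomized teen, unless permission for data collection is withdrawn.

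Reconcile this with the early-discontinuation paragraph in section 6, the ITT definition in 9.3, and the attended-one-class and complete-case rules in 9.5. Section 9.4.2 must also be reconciled with it, so that the protocol says whether withdrawal from the study under that section also ends data collection. Settle the 36- versus 44-week horizon (6.1 against 8.4).

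Section 9.5.1 describes PROMIS collection in the past tense. If collection is finished, what remains is to state the censoring rule for discontinuers and add a sensitivity analysis for informative censoring.

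The cost is protocol and consent wording, reminders, some burden on teens who have left, and continued review of incoming scores. PROMIS and SMFQ also trigger referral, so that review would run under the existing safety procedures, which this change does not alter.
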